To address questions regarding dosing both in terms of efficacy and safety, we will plan for an “early phase” of the study, which will essentially serve as a nested dose-response study. In this “early phase” we will randomize the first 45 subjects to one of 3 study arms (placebo, midodrine 10 mg thrice daily or midodrine 20 mg thrice daily). For the interim analysis of this “early phase”, a final sample size of 15 patients per group will provide 80% power to detect a 5 mcg/min decrease in norepinephrine equivalents at 24 hours.

Together with our “early phase” nested study and anticipating a 25% mortality in patients with septic shock we would need to enroll 115 patients to reach statistical significance. Enrolling 115 patients would allow randomization of 50 patients to placebo and 50 patients to the midodrine dose continued following the “early phase” (either 10 or 20 mg depending on the results of our interim analysis at which time we will evaluate both the safety and efficacy of both dosing strategies and continue the lowest dose that is both safe and efficacious). The additional 15 subjects would be required for the early dose-response portion of the study.

In brief:

115 total subjects: 50 placebo, 50 midodrine (either 10mg or 20mg); 15 additional subjects for the “early phase” portion of the study

2. Describe expected rate of screen failure/ dropouts/withdrawals from all sites.

Average mortality in septic shock is anticipated to be around 25-30%. Screen failure is anticipated to be around 20%, mostly due to patients with decompensated cirrhosis. This is based on our MICU septic shock database.

3. How many subjects will be enrolled at all sites?

149

4. How many subjects will sign a consent form under this UVa protocol?

149

Inclusion/Exclusion Criteria

1. List the criteria for inclusion

- Patients aged \geq 18-89 years old
- Admitted to UVA medical ICU with diagnosis of septic shock.
- Patients requiring at least 5 mcg/min norepinephrine infusion (or equivalent) for blood pressure support for at least 3 hours
- Patients with enteral access established within 12 hours of admission (either able to swallow, or feeding tube in place)

2. List the criteria for exclusion

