- Midodrine HCl has been used in patients concomitantly treated with salt-retaining steroid therapy (i.e., fludrocortisone acetate), with or without salt supplementation. The potential for supine hypertension exists in these patients and may be minimized by either reducing the dose of fludrocortisone acetate or decreasing the salt intake prior to initiation of treatment with Midodrine HCl.
- Alpha-adrenergic blocking agents, such as prazosin, terazosin, and doxazosin, can antagonize the effects of Midodrine HCl.

Patients will be continuously monitored in ICU and the goal of the study is to raise blood pressure.

Statistical Considerations

1. Is stratification/randomization involved?

YES

► IF YES, describe the stratification/ randomization scheme.

After enrollment, patients will initially be randomized employing a block of 9 randomization scheme generated by the study investigators. Allocation will be performed manually; there will be 5 envelopes, each envelop for a sequence of 9 patients. Each envelope will contain 3 cards for the placebo group and 3 cards for the midodrine 10 mg TID treatment group and 3 cards for the midodrine 20 mg TID treatment group. Cards will be pulled out of the envelope to randomize the patients. Once 9 patients are randomized the next envelop will be opened.

Following interim analysis of the first 45 patients, one of the treatment groups will be dropped with preference given to dropping the midodrine 20 mg TID group should interim analysis demonstrate similar, significant effect sizes in both treatment groups. Additionally, the safety profile of both dosing strategies will be considered prior to continuing the experimental arm of the study.

Subsequently, the remaining 104 patients will be randomized employing a block of 8 randomization scheme generated by the study investigators. Allocation will be performed manually; there will be 13 envelopes, each envelop for a sequence of 8 patients. Each envelope will contain 4 cards for the placebo group and 4 cards for the continuing midodrine group (either 10 mg TID or 20 mg TID). Cards will be pulled out of the envelope

to randomize the patients. Once 8 patients are randomized the next envelop will be opened.

► IF YES, who will generate the randomization scheme?

Sponsor
 UVa Statistician. Answer/Response:
 UVa Investigational Drug Service (IDS)
 Other: Answer/Response: Investigators
UVa Investigational Drug Service (IDS)

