2. What are the statistical considerations for the protocol?

We will compare placebo group versus the midodrine intervention group for all primary analyses and use the Mann-Whitney U test to assess the primary outcome, which is assumed to be non-parametric.

3. Provide a justification for the sample size used in this protocol.

To estimate the sample size, we used the UVA Clinical data repository (CDR) to identify 960 patients who would have met our study enrollment criteria (patients receiving IV vasopressors for >3 hours, with a diagnosis of sepsis, without cirrhosis, and not receiving midodrine). We then extracted their duration of vasopressors and the total norepinephrine equivalent doses at 24 hours. We performed repeated simulation of bootstrapped samples to estimate power from these populations with varying sample and effect sizes. Based on these estimates, we believe that a final sample size of 50 per group will provide 80% power to detect a 12-hour difference in duration of IV vasopressors (our primary end point) based on a 2-arm study design (placebo vs midodrine). These calculations compare favorably with those obtained assuming a normal distribution, based on a mean IV vasopressor duration of 54.9 hours (SD 28.4 h) in patients with septic shock as published in a recent trial⁹, which calculations would require randomization of 49 patients to each group to detect an effect of 18 hours difference in IV vasopressor duration at a power of 80% and an alpha value of 0.05. However, because our calculations are based on internal data (and so should reflect our practices of vasopressor weaning) and because the distribution of IV vasopressor duration is non-normal, we believe that sample size calculation based upon our CDR analysis is more accurate.

To address questions regarding dosing both in terms of efficacy and safety, we will plan for an “early phase” of the study, which will essentially serve as a nested dose-response study. In this “early phase” we will randomize the first 45 subjects to one of 3 study arms (placebo, midodrine 10 mg thrice daily or midodrine 20 mg thrice daily). For the interim analysis of this “early phase”, a final sample size of 15 patients per group will provide 80% power to detect a 5 mcg/min decrease in norepinephrine equivalents at 24 hours.

Together with our “early phase” nested study and anticipating a 25% mortality in patients with septic shock would need to enroll 149 patients to reach statistical significance.

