Secondary outcomes will include ICU and hospital length of stay as well as central venous catheter dwell time. Because IV vasopressor duration cannot be assumed to have a normal distribution, we intend to analyze our primary outcome using the Mann-Whitney U test.

4. What is your plan for primary variable analysis?

Dose of IV vasopressor(s) at 24 hours and hours requiring IV vasopressor therapy will be the primary outcomes of interest for the “early phase” and complete study, respectively. Because IV vasopressor duration and dose cannot be assumed to have normal distributions, we intend to analyze our primary outcome using the Mann-Whitney U test.

5. What is your plan for secondary variable analysis?

1. Central venous catheter free days
2. Hospital length of stay
3. Intravenous Vasopressor free days
4. 28-day mortality
5. ICU mortality
6. Need for re-initiation of vasopressor therapy after discontinuation for >2 hours

We will employ the Chi square test for binary outcomes. Furthermore, we will use regression analyses with appropriate interaction terms.

6. Have you been working with a statistician in designing this protocol?

No

IF YES, what is their name?

Answer/Response:

N/A

7. Will data from multiple sites be combined during analysis?

No

INSTRUCTIONS: IF YES, answer the following questions

7(a). Does the study involve randomization?

Answer/Response:

IF YES, will randomization be done at each site or among sites?

Answer/Response:

7(b). Has the sample size calculation considered the variation among sites?

Answer/Response:

7(c). When combining the data from multiple sites to assess the study results, is the effect of the treatment to be tested (or the association to be tested) assumed to be the same across sites or vary among sites? What is the modelling strategy?

Answer/Response:

7(d). Is there a common protocol used in all sites?

Answer/Response:

IF NO, how will differences among sites, such as those related to the implementation, inclusion criteria, patient characteristics, or other sites characteristics, be considered to assess the study results?

Answer/Response:

Study Procedures-Biomedical Research

1. What will be done in this protocol?

Screening:

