7. GCS
8. APACHE IV scores
9. Blood gas data
10. Mortality data (30- and 90-day)
11. Culture data

12. Diagnosis data pulled from provider notes
13. MAR data including concomitant corticosteroid use and antibiotics
14. Imaging data, including CXRs and CTs
15. Vital sign data including temperature, heart rates, blood pressures for the duration of the admission

The standard current ICU level care will be provided to both study groups. Invasive blood pressure measurement, laboratory studies, and imaging studies will be done according to standard practices in septic shock for all groups in the trial.

Intravenous vasopressor will be weaned in both groups as tolerated for MAP goal of > 65 mmHg by the bedside nursing staff according to usual practice (no protocolized algorithm for vasopressor weaning exists, vasopressors are weaned, as long as targeted MAPs are maintained, according to nursing judgment).

Subjects admitted to the ICU with a diagnosis of sepsis and in shock as defined, for study purposes, as requiring any IV vasopressor of at least 5 mcg/min norepinephrine infusion (or equivalent) for at least 3 hours AND with adequate enteral access (oral, orogastric, nasogastric or pre-existing PEG) will be randomized to either midodrine 10 or 20 mg every 8 hours for 72 hours or placebo, to investigate the efficacy of midodrine in decreasing time to IV vasopressor liberation in patients with septic shock. Data collection will continue until hospital discharge.

A dose of up to 20 mg TID is chosen as it was the modal dose in a recent prospective study and is the upper end of dosing with predictable hemodynamic response in another study. The retrospective studies previously referenced reported varying doses up to 40 mg TID.

The standard current ICU level care will be provided to both study groups. Invasive blood pressure measurement, laboratory studies, and imaging studies will be done according to standard practices in septic shock for both arms of trial. Intravenous vasopressor will be weaned in both groups as tolerated for MAP goal of > 65 mmHg by the bedside nursing staff.

2. If this protocol involves study treatment, explain how a subject will be transitioned from study treatment when they have completed their participation in the study.

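### The final Mann-Whitney test pools two separately randomised phases without stratifying by phase: a valid test for placebo versus the continuing dose, but one that a phase-stratified rank test would improve at almost no cost

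*Combined protocol and SAP*

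**What the plan says.** Statistical Considerations, item 1, sets out two schemes in sequence. At first, "patients will initially be randomized employing a block of 9 randomization scheme". There are five envelopes, and "Each envelope will contain 3 cards for the placebo group and 3 cards for the midodrine 10 mg TID treatment group", with three more for 20 mg. After the interim analysis one dose is dropped and "the remaining 104 patients will be randomized employing a block of 8 randomization scheme". There are 13 envelopes, and "Each envelope will contain 4 cards for the placebo group and 4 cards for the continuing midodrine group".

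The intended final comparison appears in the summary count under Human Participants, Subjects item 1: "115 total subjects: 50 placebo, 50 midodrine (either 10mg or 20mg); 15 additional subjects" for the early phase. The analysis sections do not repeat it. Statistical Considerations, item 2, compares placebo with a midodrine group that it does not define further, and will "use the Mann-Whitney U test to assess the primary outcome". Item 4 makes hours on IV vasopressors the primary outcome of the complete study and says "we intend to analyze our primary outcome using the Mann-Whitney U test".

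No analysis names phase. Item 5 mentions regression with interaction terms, but for secondary outcomes and without listing the terms. Study Procedures, item 1, says of vasopressor weaning that "no protocolized algorithm for vasopressor weaning exists".

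**The concern.** The two phases run one after the other, with an interim analysis between them. The outcome depends on when nurses wean, and weaning follows judgement. If typical vasopressor duration shifts between patients 1-45 and patients 46-149, ranking everyone together treats that shift as random variation between patients. The test then works below its nominal 5% and loses power for the 12 h target. The trial already randomises within phase, so analysing within phase would remove this loss and compare only patients randomised concurrently.

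A second issue is tied to the first. The effect of a shift depends on who is in the midodrine group, and the analysis sections leave that open.

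**Working it through.** **1. The plan's counts.** Item 3 gives 50 per arm, 25% mortality and 149 enrolled.
- 50 / 0.75 = 66.7, so 67 per arm; 2 × 67 + 15 = 149 = 45 + 104. The total reproduces.
- Early phase: 5 × 9 = 45, or 15 per arm. Later phase: 13 × 8 = 104, or 52 per arm. 15 + 52 = 67.
- After 25% loss: 15 × 0.75 = 11.25 and 52 × 0.75 = 39, so about 11 + 39 = 50 evaluable per arm.

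So early placebo and continuing-dose patients are in the final comparison, and the 15 on the dropped dose are not. The stated 80% power for 12 h rests on repository data that the documents do not give, so it cannot be reproduced.

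**2. Bias.** For placebo versus the continuing dose, allocation is 15:15 and then 52:52. Phase is balanced across arms by design, so a shift does not bias the comparison.

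**3. Size by hand.** As an approximation on means, let p = 15/67 = 0.224 be the early share of each arm and d the shift. Pooling adds p(1 − p)d² = 0.174 d² to the variance of 28.4² = 806.6. The true two-sided size is then about 2[1 − Φ(1.96 √(1 + 0.174 d²/806.6))].

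| Shift d | Added variance | Approximate size |
|---|---|---|
| 6 h | 0.8% | 4.9% |
| 12 h | 3.1% | 4.7% |
| 24 h | 12.4% | 3.8% |

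Simulated Mann-Whitney sizes with normal durations and 15 + 52 per arm were 4.9%, 4.5% and 3.75%.

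**4. Power by simulation.** Assumptions: lognormal hours with the printed mean and SD, a 12 h effect, an additive shift in the early phase, two-sided 0.05, 11 + 39 per arm, 20,000 trials per case. The stratified test is van Elteren's, which sums the within-phase rank sums with weights 1/(N_h + 1).

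| Shift | Pooled power | Stratified power | Pooled size |
|---|---|---|---|
| 0 h | 72.0% | 71.8% | 4.9% |
| 6 h | 71.5% | 71.7% | not run |
| 12 h | 69.7% | 71.8% | 4.3% |
| 24 h | 64.1% | 72.5% | 3.4% |

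The rows combine separate runs. The stratified size stayed at about 5.0%. Repeat runs gave gains of 2.1 to 2.2 points at 12 h and 8.3 to 8.6 at 24 h, and losses of 0.2 to 0.5 with no shift. With 15 + 52 per arm the gains were 1.7 to 1.8 and 6.7 to 7.2 points. If shift and effect are both proportional, the gains fall to 0.4-0.6 points at 12 h and 2.4-2.9 at 24 h.

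**5. If both doses counted as midodrine.** Allocation would be 15:30 early and 52:52 later. The early share would be 15/67 = 22.4% on placebo and 30/82 = 36.6% on midodrine, a difference of 14.2 percentage points. A 12 h shift would then create a spurious difference in means of 0.142 × 12 = 1.7 h, and a 24 h shift 3.4 h. Simulated size of the pooled test is 6.3% at 12 h and 9.9% at 24 h; the stratified test stays at 4.8 to 4.9%.

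**The case against.** The strongest objection is that the shift is hypothetical, and much of this stands. The documents describe one medical ICU, one blood-pressure goal throughout, and blinding of nurses and investigators. The lack of a weaning algorithm implies variation between patients, not a systematic change after patient 45. Nor does the fall in the share on active drug, from two in three to one in two, by itself change durations on placebo or on the continuing dose. A 12 h shift is already as large as the target effect. A 24 h shift is 44% of the printed mean (24/54.9), and the large gain there also needs the additive model.

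A reader might infer that any drift costs power. In direction it adds noise, but up to about 6 h the two tests cannot be told apart.

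A reader might also infer that the planned test is conservative in this trial. That describes drift alone, with dropped-dose patients excluded. The participant count implies exclusion, but the analysis sections do not state it, and step 5 shows the opposite result if both doses are pooled. Choosing the dose on early data and then reusing those patients also raises the error in midodrine's favour. In simulation this reached at most about 3.7% against 2.5% one-sided, with no drift and the dose chosen on a measure perfectly correlated with final duration. Drift offsets this only in part, and stratifying does not correct it.

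What survives is that the change costs almost nothing and protects under either reading of the midodrine group.

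**Conclusion.** The point holds as a minor efficiency improvement. The plan pools two separately randomised phases in an unstratified rank test. For placebo versus the continuing dose that test is valid and is not biased by drift, so the omission does not threaten the trial's conclusion. Its size depends entirely on an assumed shift: nothing of practical weight up to about 6 h, about 2 points of power at 12 h, and 7 to 9 points at 24 h if additive (about 0.5 and 2.5 to 3 if proportional). These figures rest on lognormal durations with the published mean and SD, not on the trial's own repository data.

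Leaving the midodrine group undefined adds a reason to act. If both doses were pooled, the unstratified test's type I error would rise to about 6% at a 12 h shift and 10% at 24 h, while the stratified test would stay near 5%. The documents' counts point away from that reading, so this is an ambiguity to close, not an error to charge. The dose-selection issue is separate.

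**What to change.** In Statistical Considerations, items 2 and 4, state that the final primary analysis compares placebo with the continuing dose only, leaving out patients on the dropped dose. Specify a Wilcoxon (van Elteren) test stratified by randomisation phase (first 45 versus remaining 104), and keep the plain Mann-Whitney as a sensitivity analysis. Settle this before the final data are unblinded, so that the choice of test cannot follow the result.

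The cost is one sentence and at most about half a point of power if there is no shift. Phase is known from the order of randomisation, so no new data, patients or procedures are needed. Carrying phase into the secondary analyses, as a stratum for the binary outcomes and a term in the regressions, is optional; no gain was calculated for it.

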Study Design: Biomedical

1. Will controls be used?

Yes

► IF YES, explain the kind of controls to be used.

The control group will receive placebo on the same schedule that the investigational agent is administered, namely every 8 hours for 72 hours. The placebo will be prepared by our investigational pharmacy and dispensed by the same.

2. What is the study design?

Randomized, Double-Blind Placebo-Controlled Trial

3. Does the study involve a placebo?

Yes

► IF YES, provide a justification for the use of a placebo

Placebo is justified to provide for blinding of the nursing staff and study investigators who might otherwise confound study results by weaning vasopressors more or less aggressively than usual practice.

Human Participants

Ages: 18-89 years of age

Sex: BOTH

Race: ANY

Subjects- see below

1. Provide target # of subjects (at all sites) needed to complete protocol.

To estimate the sample size, we used the UVA Clinical data repository (CDR) to identify 960 patients who would have met our study enrollment criteria (patients receiving IV vasopressors for >3 hours, with a diagnosis of sepsis, without cirrhosis, and not receiving midodrine). We then extracted their duration of vasopressors and the total norepinephrine equivalent doses at 24 hours. We performed repeated simulation of bootstrapped samples to estimate power from these populations with varying sample and effect sizes. Based on these estimates, we believe that a final sample size of 50 per group will provide 80% power to detect a 12-hour difference in duration of IV vasopressors based on a 2-arm study design (placebo vs midodrine). These calculations compare favorably with those obtained assuming a normal distribution, based on a mean IV vasopressor duration of 54.9 hours (SD 28.4 h) in patients with septic shock as published in a recent trial⁹, which calculations would require randomization of 49 patients to each group to detect an effect of 18 hours difference in IV vasopressor duration at a power of 80% and an alpha value of 0.05. However, because our calculations are based on internal data (and so should reflect our practices of vasopressor weaning) and because the distribution of IV vasopressor duration is non-normal, we believe that sample size calculation based upon our CDR analysis is more accurate.

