Patients admitted to the ICU with a diagnosis of sepsis and in shock as defined, for study purposes, as requiring any IV vasopressor of at least 5 mcg/min norepinephrine infusion (or equivalent) for at least 3 hours AND with adequate enteral access (oral, orogastric, nasogastric or pre-existing PEG, will be screened by research nurse, study coordinator or study investigator by review of medical record in EPIC only. If subject meets study criteria then the research nurse, study coordinator or investigators will approach patient or surrogate for consent to participate in the study. For patients unable to provide consent due to illness, surrogate consent will be sought.

Following consent, women of childbearing potential will have a urine pregnancy test. Pregnant women will be excluded.

Study Treatment:

In the “early phase” the first 45 subjects will be randomized to one of 3 study arms (placebo, midodrine 10 mg or midodrine 20 mg thrice daily for 72 hours). The remaining 104 subjects will subsequently be randomized to one of 2 study arms, placebo or the more efficacious of the 2 midodrine doses (10 mg TID or 20 mg TID) as determined by the planned interim analysis.

Data collection from the subject’s medical record will continue until hospital discharge. Data to be collected will include the following:

1. Vasopressor(s) used by type
2. Vasopressors dose and duration
3. ICU and hospital length of stay
4. Basic lab values including CBC, makers of renal function, cardiac biomarkers (troponin, BNP)
5. Presence of central venous catheter, site and number
6. CVC dwell time

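### The final test appears to re-use the 15 early-phase patients whose data helped choose the dose, with no allowance for that choice; the effect is modest and depends on which of three selection rules applies

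*Combined protocol and SAP*

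**What the plan says.** The first 45 patients are randomised equally to placebo, midodrine 10 mg or midodrine 20 mg. An interim analysis drops one midodrine arm, and 104 further patients go 1:1 to placebo or the kept dose (Statistical Considerations, item 1). Item 4 makes the 24-hour vasopressor dose the early-phase primary outcome and vasopressor hours the primary outcome of the complete study.

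Item 2 gives the final analysis: "We will compare placebo group versus the midodrine intervention group for all primary analyses and use the Mann-Whitney U test". Item 3 gives its size: "a final sample size of 50 per group will provide 80% power to detect a 12-hour difference in duration of IV vasopressors", and adds that this is for a two-arm design. An alpha of 0.05 appears only in the normal-theory cross-check, and its sidedness is not stated.

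Human Participants, item 1, explains the total of 115 as "randomization of 50 patients to placebo and 50 patients to the midodrine dose continued following the" early phase, plus 15 further subjects for the dose-response portion.

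The selection rule appears in three forms:

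- Human Participants, item 1: the lowest dose found safe and efficacious continues.
- Statistical Considerations, item 1: one arm is dropped, preferably 20 mg if both effects are similar and significant.
- Study Procedures, Study Treatment: patients go to "placebo or the more efficacious of the 2 midodrine doses (10 mg TID or 20 mg TID) as determined by the planned interim analysis".

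No section adjusts for having chosen between two doses, and none describes a power calculation that includes the choice.

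**The concern.** When the better-looking of two arms is kept, its first patients are on average a lucky sample. If they are pooled with the later patients and tested as though the dose had been fixed in advance, that luck enters the final comparison. Chance results in favour of midodrine become more frequent, and the estimated hours saved are too large on average.

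The stated power is a separate matter. The trial may carry forward the less effective dose, and a two-arm calculation cannot reflect that.

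**Working it through.** **1. Who is in the final comparison.** Of 115 patients, 115 − 45 = 70 come after the interim, or 35 per arm. Reaching 50 per arm needs 35 + 15. For 149: 50/0.75 = 66.7, rounded up to 67; 104/2 = 52; 52 + 15 = 67; and 2 × 67 + 15 = 149. Both totals therefore count the 15 early-phase patients on placebo and the 15 on the kept dose.

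**2. The plan's own power.** The 80% for 12 hours cannot be reproduced, because the repository distribution is not in the documents. With the only SD given (28.4 h), power at 50 per group is Φ(12/(28.4 × √(2/50)) − 1.96) = Φ(2.11 − 1.96) = 56%. That is a separate question. Below, the effect is set so that a fixed trial of 50 per arm has exactly 80% power: d = (1.96 + 0.84) × √(2/50) = 0.560 SD.

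**3. Bias with no drug effect, better dose kept.** The expected maximum of two independent standard normals is 0.564, so

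bias = [n₁/(n₁ + n₂)] × ρ × 0.564 × SD/√n₁,

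where n₁ = 15, n₂ = 35 or 52, SD = 28.4 h, and ρ is the correlation between 24-hour dose and hours (not given; assumed 0.4 to 1.0).

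- 15 + 35, ρ = 1: 0.30 × 0.564 × 28.4/3.873 = 1.24 h. At ρ = 0.4: 0.50 h.
- 15 + 52, ρ = 1: 0.224 × 0.564 × 28.4/3.873 = 0.93 h. At ρ = 0.4: 0.37 h.

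**4. False claim of benefit.** Simulation under a normal model: three arms of 15, choose a dose, add 35 or 52 per arm, test the pooled data at |Z| > 1.96 (0.05 taken as two-sided).

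| Rule | Benefit-direction error | Total two-sided error | Bias |
|---|---|---|---|
| Better dose kept, ρ 0.4 to 1.0 | 2.9% to 3.7% | 5.0% | 0.4 to 1.2 h |
| Lower dose kept unless only the higher is significant | 2.5% to 2.8% | at most about 5.3% | under 0.1 h |

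A Mann-Whitney check on skewed (gamma) durations with mean 54.9 h and SD 28.4 h gave 3.0% to 3.6% for the first rule at ρ 0.5 to 1.0. If the 0.05 were one-sided, it would become 6.0% to 7.2% over the same correlations.

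**5. Power, 15 + 35 per arm, better dose kept, d = 0.560 SD on both outcomes.** If only one dose works, it is chosen with probability Φ(0.560/√(2/15)) = Φ(1.53) = 94%. If the other has half the effect, the better dose is chosen with probability Φ(0.280/0.365) = 78%.

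| True effects | Unadjusted, ρ 0.5 / 1.0 | Critical value 2.13, ρ 0.5 / 1.0 |
|---|---|---|
| Both doses full | 83.0% / 86.1% | 78.2% / 81.8% |
| One full, one none | 75.8% / 76.5% | 70.8% / 71.6% |
| One full, one half | 71.3% / 74.0% | 66.0% / 68.8% |

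Over ρ 0.4 to 1.0 the unadjusted ranges are about 82% to 86%, 76% to 77% and 71% to 74%. If the 24-hour effect is weaker than the effect on hours, the right dose is chosen less often: shrinking it by ρ = 0.6 gives about 68% in the one-dose case.

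**6. Critical value.** Holding 2.5% in the benefit direction at ρ = 1 with the better dose kept needs Z of about 2.12 (15 + 52) or 2.13 (15 + 35).

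**The case against.** - **Pooling is inferred.** No section says that early-phase patients enter the final test, and the midodrine intervention group is undefined. If it meant post-interim patients only, or all midodrine patients on either dose, the selection effect would vanish. This stands as a caveat. However, the first reading leaves 35 per arm against a planned 50, and the second conflicts with setting 15 subjects apart as additional. The group needs defining in any case.
- **The effect is small and depends on the rule.** This also stands. The upper figures need a correlation of 1.0 and the better-dose rule; a lower-dose default nearly removes the problem. A rule that keeps 10 mg if significant and otherwise the better dose brings the inflation back. Stopping when neither dose beats placebo numerically would give 2.2% to 3.3% (15 + 52), but no such rule is written.
- **Total alpha.** A reader might infer that the two-sided error exceeds 5%. Under the better-dose rule it does not: the harm tail shrinks as the benefit tail grows. Under the lower-dose default the excess is at most about 0.3 points.
- **Power.** A reader might infer that the 80% holds only if both doses work fully. In that case power is above 80%. The losses arise when the doses differ, come from sometimes choosing the weaker one, and would occur in any dose-selection trial. Adjusting alpha does not cure them.

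**Conclusion.** The point holds, at modest size. On the only reading that fits both totals, the final test re-uses patients whose data helped choose the dose and makes no allowance for it. Under the better-dose rule the false-benefit rate is about 2.9% to 3.7% instead of 2.5%, with an upward bias of 0.4 to 1.2 hours, or 3% to 10% of the 12-hour target. Under a lower-dose default both effects are close to negligible. The stated 80% is not the power of the design to be run, which may lie above or below it.

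These figures rest on the inferred pooling, a two-sided 0.05, an assumed correlation (at zero there is no inflation) and no early stop. Exact operating characteristics cannot be given until the three rules agree. The documents do not support calling this a breach of 5% overall error, or saying that a formal closed testing procedure is required.

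**What to change.** 1. Reconcile the three statements of the selection rule, including what happens if neither dose qualifies. Which rule to adopt is for the sponsor.
2. State that the final analysis set is the selected midodrine arm plus placebo, from both stages.
3. Re-run the repository simulation with the selection step included, and restate the 80%. The extraction already holds 24-hour dose and duration for the same 960 patients, so their correlation can be estimated there. Use the same runs to set the critical value for the pooled Mann-Whitney test that holds 2.5% in the benefit direction under the reconciled rule. The ceiling is about 2.12 (2.13 at 15 + 35), the worst case under the better-dose rule.
4. Report the post-interim-only estimate beside the pooled one. It is free of the selection effect but less precise: as the sole test with 35 per arm, power would be Φ(0.560 × √(35/2) − 1.96) = 65%. It therefore belongs as a supporting estimate.

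Cost: protocol wording, one re-run of an existing simulation and no extra patients. The stricter critical value costs up to about 4 to 5 points of power against the unadjusted test, and less if the correlation is lower or the reconciled rule selects less strongly.
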